#### 8.3 Subject Withdrawal

If a subject wishes to leave the study at any time, they will be permitted to do so. Every reasonable effort will be made by Quotient Sciences to complete a final assessment/discharge procedures. Quotient Sciences will advise the sponsor of the withdrawal of any subject from the study.

Early withdrawal is defined as the date of the decision to withdraw the subject from the study. Subject completion is defined as the date of the last procedure conducted or last contact (ie phone call) for that subject.

If a subject requests to leave the clinical unit earlier than the planned discharge time eg due to unforeseen personal circumstances, but aims to return to the clinical unit to complete the study, this will be documented as a subject self-discharge and a protocol deviation. The subject must complete the planned assessments/discharge procedures before discharge from the clinical unit and will return for the next assessments, as planned.

Subjects will be withdrawn from the study drug(s) for the following reasons:

- Experiencing a serious or severe AE including but not limited to:
  - QTcF interval of >500 msec or increase in QTcF interval of >60 msec from baseline (confirmed following a repeat ECG after 10 min in resting position)
  - ALT concentration >3 × the upper limit of the reference range (confirmed following a repeat ALT blood test)
- Experiencing a 25% decrease in CLcr
- Pregnancy
- Concurrent illness or requirement for prohibited medication
- At the discretion of the investigator

Subjects will be withdrawn from the study for the following reasons:

- Termination of the study
- Upon the subject's request (withdrawal of consent)
- Significant deviation from the protocol

For the purpose of QTcF withdrawal criteria, baseline will be considered as the average of the pre-dose Day 1 triplicate measurement. For the purpose of CLcr and ALT withdrawal criteria, baseline will be considered as the admission Day -1 measurement.

For a subject who withdraws because of an IMP-related AE, every effort will be made to ensure the subject completes follow-up procedures. Any subject withdrawn or discontinuing the study prematurely because of an IMP-related AE or termination of the study will be considered to have completed the study, and will not be replaced.

Subjects withdrawing for other reasons may be replaced at the discretion of the investigator and sponsor.

#### 8.4 Subject Replacement

Up to 16 (2 per cohort) replacement subjects may be enrolled into the study. The maximum number of subjects that may be dosed is 80.

Subjects withdrawn due to a IMP-related AE or termination of the study will be considered to have completed the study, and will not be replaced.

Subjects who are withdrawn for other reasons may be replaced at the discretion of the investigator and sponsor to ensure sufficient evaluable subjects.

Replacement subjects enrolled will be dosed with the same regimen as the subject they replace.

An evaluable subject is defined as a subject who has sufficient PK and safety data up to 72 h post-dose or was withdrawn prior to 72 h due to an adverse event.

#### 8.5 Stopping Criteria

The study will be halted, and the risk to other subjects evaluated if any of the following criteria are met:

- A serious adverse reaction (ie, a SAE considered at least possibly related to the IMP administration) in one subject.
- Severe non-serious adverse reactions (ie, severe non-serious AE considered as, at least possibly related to the IMP administration) in two subjects in the same cohort, independent of within or not within the same system organ class.

Relatedness will be determined by the investigator. For SAEs the Sponsor will make a parallel assessment; please refer to Section 14.5.2.

If the study is halted, a temporary halt will be submitted to the Medicines and Healthcare products Regulatory Agency (MHRA) and EC in the form of a substantial amendment. The study may be resumed or terminated; however, it will not be resumed until a further substantial amendment to resume the study is submitted and approved by MHRA and EC.

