#### 8.2.1 Criteria for Dose Escalation

Progression to the next dose group will be permitted after review of safety and PK data suggests that it is safe to do so. Dose increases will only be made after a complete review of all data collected from the previous dose group by a SRC as defined in the SRC charter. The SRC will always comprise at a minimum the investigator, the sponsor's medical responsible and a PK expert where appropriate. Full description of the SRC activities will be part of a SRC Charter implemented before the dosing of the first volunteer.

Each dose cohort will be split into 2 groups, a sentinel group (1 subject on active treatment, 1 subject on placebo), and a main group (5 subjects on active treatment, 1 on placebo). The decision to proceed with the main group will be made by the investigator, based on safety data until 24 h post-dose of the second sentinel subject (see also Section 8.5 for stopping criteria). The investigator will inform the sponsor of any safety concerns.

For dose escalation (or reduction, see below) to proceed, data must be available from a minimum of 6 subjects who have completed the planned safety assessments up to 48 h after dosing and the planned PK assessments up to 48 h after dosing to ensure at least 4 subjects had received active IMP.

The following data are required:

- AEs (mandatory)
- Vital signs
- Safety laboratory, specifically renal function parameters
- ECG
- Physical examinations
- Plasma concentrations of DNDI-0690
- Interim PK parameter estimations: AUC and Cmax

The time points for Troponin I sample collection may be altered based on emerging data from previous cohorts.

Data provided by Quotient Sciences will be provided to the SRC in accordance with the Quotient Sciences standard operating procedure (SOP) on interim dose decision making and dose escalation and as described in the SRC Charter. The decision will be documented and signed by the PI as per Quotient Sciences current SOP and by the DNDi representative as described in the SRC Charter. Evidence of the decision will be retained in the ISF.

Dose escalation will not occur if:

• A serious adverse reaction (ie, a serious adverse event [SAE] considered at least possibly related to the IMP administration) occurs in one subject.

Or

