#### 8.6 Study Termination

After the start of protocol activities but prior to the commencement of dosing, the study may be terminated by the sponsor and investigator without consultation with the MHRA and EC. The end of the trial must be notified to the MHRA and EC immediately and at the latest within 15 days after the study is terminated, clearly explaining the reasons. A description of follow-up measures taken for safety reasons if applicable, will also be provided.

If the study is abandoned prior to commencement of any protocol activities, the PI or sponsor must notify the EC and MHRA by letter outlining the reasons for abandonment of the trial.

Once exposure to dosing has begun, the study will be completed as planned unless the following criteria are satisfied that require a temporary halt or early termination of the study.

• The occurrence of serious or severe adverse event(s), as defined in Section 8.5, if considered to be related to the IMP, as defined in Section 14.5.

- New information regarding the safety of the IMP that indicates a change in the risk/benefit profile for the compound, such that the risk/benefit is no longer acceptable for subjects participating in the study.
- Significant violation of Good Clinical Practice (GCP) that compromises the ability to achieve the primary study objectives or compromises subject safety.

If any of the above occurs, the study will be terminated if careful review of the overall risk/benefit analysis described in Section 6.4 demonstrates that the assumptions have changed and that the overall balance is no longer acceptable. In these circumstances termination can only take place with the agreement of the investigator and sponsor. The MHRA and EC will be informed of study termination.

If it becomes necessary to consider termination of the study after dosing has begun, dosing may be suspended pending discussion between the investigator and sponsor. Dosing will be stopped immediately on safety grounds.

The study may be terminated early or suspended at the request of the MHRA or EC.

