#### 14.1.6 Suspected Unexpected Serious Adverse Reactions (SUSARs)

SUSARs are SAEs which are believed to be related to an IMP and are both unexpected (ie the nature or severity is not expected from the information provided in the IB) and serious. SUSARs are subject to expedited reporting to the MHRA, EMA and EC (see Section 16.3.2 for details on reporting SUSARs).

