#### 14.5.2 By the Sponsor

The Investigator is responsible for assessing seriousness and relatedness of an AE. In parallel, the Sponsor will also evaluate the seriousness of all events which are reported to him by the Investigator, and the causality of the study drug for each AE. The Investigator's decision will be independent of the Sponsor's.

AEs for which the Investigator consider that a causal link with the study product is a reasonable possibility will be considered to be suspected adverse effects. Should the evaluations of the Sponsor and the Investigator differ with regard to causality and the event being serious, then both will be reported in the declaration of suspected adverse reactions.

The Sponsor is responsible for determining the expectedness of the SAE, using the IMP reference safety information. Each SAE has to be classified by the sponsor as expected or unexpected for the IMP.

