#### 16.3.2 Reporting of SUSARs

The Sponsor is responsible for all declarations to Health Authorities (EMA/MHRA) as described in this protocol and in the Safety Management Plan. Quotient is responsible to inform the Sponsor of any update/modification of the local requirements.

It is the responsibility of the sponsor to determine whether a reported SAE fits the classification of a SUSAR and to notify the investigator of their decision as soon as possible.

The Sponsor (represented by the pharmacovigilance service provider [United BioSource Corporation] by delegation) is responsible for reporting SUSARs to the EC.

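### The one-SAE halt follows the investigator's causality grade: a sentinel SAE that only the sponsor suspects triggers no stated halt, and the main group need not wait for the sponsor's view

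*Protocol*

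**What the plan says.** Section 8.5 lists two events that halt the study. The first is a single SAE regarded as at least possibly related to the drug. On who judges this, it states "Relatedness will be determined by the investigator. For SAEs the Sponsor will make a parallel assessment", and refers to section 14.5.2.

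Section 14.5.2 has the sponsor assess seriousness "and the causality of the study drug for each AE", and describes the investigator's judgement as independent of the sponsor's. On disagreement it says "Should the evaluations of the Sponsor and the Investigator differ with regard to causality and the event being serious, then both will be reported".

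Within a cohort, section 8.2.1 says: "The decision to proceed with the main group will be made by the investigator, based on safety data until 24 h post-dose", with the time counted from the later of the two sentinel doses. It points to section 8.5 and asks the investigator to tell the sponsor about safety concerns. Section 8.1 lets the Principal Investigator or a medically qualified designee take the decision, and sets 24 h after the second sentinel dose as the earliest time for the first main-group dose.

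**The concern.** The protocol creates two independent causality views on every SAE but attaches the halt to only one of them. This matters most for the grade of probably not related. Section 14.5 uses that grade where a link with the drug remains possible but another cause is more likely, and counts it as not related. An investigator can therefore leave a drug effect open and still not meet the section 8.5 criterion. This is also where a sponsor assessor could most plausibly settle one grade higher, on possibly related.

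At sentinel release the stake is direct. Only one person in the cohort has had active drug at that point, and the next step exposes five more to the same dose. Between cohorts, the safety review committee that decides on escalation includes the sponsor's medical responsible. Release within a cohort has no equivalent requirement.

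**Working it through.** The plan gives no statistical figure to reproduce. The check sets the provisions side by side and adds two small pieces of arithmetic.

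**1. What each combination of views leads to.** From section 14.5, possibly, probably and definitely related count as related; probably not related and not related count as not related. I assume that the sponsor uses the same scale.

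| Investigator | Sponsor | Halt under 8.5 | Main group under 8.1 and 8.2.1 |
|---|---|---|---|
| At least possibly related | Any view | Required | Not dosed while halted |
| Not or probably not related | Not or probably not related | Not triggered | Investigator may release |
| Not or probably not related | At least possibly related | No stated trigger; both views reported (14.5.2) | Investigator may release |

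The third row is the gap. No section says that a sponsor-only suspicion halts dosing.

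**2. Exposure per release.** From sections 8.1 and 8.8.2:

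- Sentinel group: 1 active + 1 placebo = 2 subjects.
- Main group: 5 active + 1 placebo = 6 subjects.
- Cohort: 2 + 6 = 8 subjects, of whom 1 + 5 = 6 are on active drug.
- Share of active doses given after the sentinel step: 5/6 = 83.3%.

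**3. Timing.** Let the investigator learn of the SAE *t* hours after the second sentinel dose. The outer limit for notifying the sponsor in section 16.3.1 is 24 h from awareness, which is *t* + 24 h after that dose. The main group may be dosed from 24 h. For any *t* > 0, *t* + 24 > 24, so the outer limit falls after the earliest main-group dose. Section 16.3.1 also asks for an immediate telephone call and notice on the day of discovery, which should make the real interval much shorter. These are duties to notify, however. No deadline is set for the sponsor's causality assessment, and release is not conditional on it.

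**The case against.** A reader might infer more than the protocol supports, in four ways.

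- **That 8.5 and 8.6 conflict.** Section 8.6 speaks of events "if considered to be related to the IMP, as defined in Section 14.5", and section 14.5 contains the sponsor's assessment. But the same bullet in 8.6 first takes its events from section 8.5. Section 14.5 names the investigator as causality assessor and uses the same threshold of possible or higher, and section 8.5 itself cites 14.5.2. The two sections rest on the same assessors and the same standard.
- **That the SUSAR provisions conflict with 8.5.** Section 14.1.6 says "SUSARs are SAEs which are believed to be related to an IMP", and section 16.3.2 says "It is the responsibility of the sponsor to determine whether a reported SAE fits the classification of a SUSAR". These govern expedited reporting. They are not a rival halt rule.
- **That the main group can be released after any sentinel SAE.** It cannot. The grade of possibly related already covers an event explained equally well by another cause, and an SAE with that grade or higher halts the study. Release requires the investigator to have judged it not or probably not related.
- **That 8.2 forbids release by the investigator.** Section 8.2 opens with a general rule that in-study decisions include sponsor staff, but 8.1 and 8.2.1 assign sentinel release specifically, and the specific rule governs.

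There are also real safeguards: immediate notice of SAEs (16.3.1), optional suspension of dosing while investigator and sponsor discuss termination (8.6), the statement "Dosing will be stopped immediately on safety grounds" (8.6) and urgent safety measures (16.2). The SRC Charter and the Safety Management Plan are not shown and may add a procedure. Finally, 83% is simply the allocation in every cohort; it does not measure how often the gap would matter.

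All of this stands, and it removes any claim of contradiction. It does not supply the missing rule. The suspension in 8.6 is discretionary, the stop on safety grounds defines neither the grounds nor who decides, and no safeguard in the protocol holds the main group until the sponsor's view is known.

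**Conclusion.** The point holds as a weakness in a stated rule. Section 8.5 assigns relatedness to the investigator, and the sponsor's parallel assessment has no stated effect on the halt. A sentinel SAE that the investigator grades as not or probably not related, but that the sponsor suspects, triggers no mandatory halt, and the main group can be dosed without the sponsor's assessment.

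Per event, this puts 6 subjects at the same dose, 5 on active drug, from 24 h after the second sentinel dose. One of the two sentinel subjects is on placebo, so the SAE may not have followed active drug at all. How often the situation would arise cannot be estimated from the protocol. The conclusion assumes that the unseen Charter and Safety Management Plan do not already hold the main group; even if they do, a stopping rule and its decider belong in the protocol. This is a cheap improvement worth making.

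**What to change.** Add to section 8.5: *For the first criterion, an SAE counts as related if either the investigator or the sponsor considers it at least possibly related.*

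Add to section 8.2.1: *After any SAE in a sentinel subject, the main group is not dosed until the sponsor's causality assessment is recorded.*

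This is a new rule, not a restatement of section 8.6, which contains no either-party provision. It costs two sentences in a protocol amendment. In operation it may cause an extra temporary halt, which under section 8.5 needs an approved substantial amendment before dosing resumes, and a short delay to main-group dosing after a sentinel SAE. The extra halt would arise only for an event that the sponsor itself considers at least possibly related. Section 8.2.1 records a committee decision taken after Cohort 5, so the change would reach only cohorts not yet dosed.

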#### 8.6 Study Termination

After the start of protocol activities but prior to the commencement of dosing, the study may be terminated by the sponsor and investigator without consultation with the MHRA and EC. The end of the trial must be notified to the MHRA and EC immediately and at the latest within 15 days after the study is terminated, clearly explaining the reasons. A description of follow-up measures taken for safety reasons if applicable, will also be provided.

If the study is abandoned prior to commencement of any protocol activities, the PI or sponsor must notify the EC and MHRA by letter outlining the reasons for abandonment of the trial.

Once exposure to dosing has begun, the study will be completed as planned unless the following criteria are satisfied that require a temporary halt or early termination of the study.

• The occurrence of serious or severe adverse event(s), as defined in Section 8.5, if considered to be related to the IMP, as defined in Section 14.5.

- New information regarding the safety of the IMP that indicates a change in the risk/benefit profile for the compound, such that the risk/benefit is no longer acceptable for subjects participating in the study.
- Significant violation of Good Clinical Practice (GCP) that compromises the ability to achieve the primary study objectives or compromises subject safety.

If any of the above occurs, the study will be terminated if careful review of the overall risk/benefit analysis described in Section 6.4 demonstrates that the assumptions have changed and that the overall balance is no longer acceptable. In these circumstances termination can only take place with the agreement of the investigator and sponsor. The MHRA and EC will be informed of study termination.

If it becomes necessary to consider termination of the study after dosing has begun, dosing may be suspended pending discussion between the investigator and sponsor. Dosing will be stopped immediately on safety grounds.

The study may be terminated early or suspended at the request of the MHRA or EC.

#### 8.7 Lost to Follow-up

A subject will be considered lost to follow-up if they fail to return for scheduled visits and cannot be contacted by the clinical unit.

If a subject fails to return to the clinical unit for a required study visit:

- The clinical unit must attempt to contact the subject and reschedule the missed visit as soon as possible
- Before a subject is deemed lost to follow-up, the investigator or designee must make every effort to regain contact with the participant (eg 3 telephone calls on 3 separate occasions and, if necessary, an email or letter to the participant's last known email/postal address). These contact attempts should be documented in the subject's source
- If the subject cannot be contacted, they will be considered lost to follow-up

#### 8.8 Randomisation

This is a double-blind, randomised, single centre, parallel-group, single-dose, doseescalation, placebo-controlled study; therefore, a randomisation schedule will be produced.

The original randomisation schedule and proof of quality control (QC) procedures will be held by the Data Sciences department at Quotient Sciences until the study is archived, at which time the randomisation materials will be retained in the ISF.

Subjects will be randomised immediately before dosing.

#### 8.8.1 Subject Numbers

Subject numbers will be allocated on the morning of dosing according to the code 001 to 064 using the lowest number available. Replacement subjects will be allocated subject numbers 901 to 964, where the last 2 digits are the same as those of the original subject (eg if Subject 005 withdraws, the replacement will have Subject Number 905 and will receive the same regimen as Subject 005).

Subject numbering by cohort is provided in Table 3.

#### Table 3Subject Numbers by Cohort

Cohort	Subject Numbers	
1	001 to 008	
2	009 to 016	
3	017 to 024	
4	025 to 032	
5	033 to 040	
6	041 to 048	
7	049 to 056	
8	057 to 064	

Each cohort will be split into 2 groups (sentinel and main), see Section 8.1 for details.

#### 8.8.2 Treatment Allocation

Using a computer-generated randomisation schedule, subject numbers will be allocated to treatment in a 3:1 ratio. The allocation for the sentinel group of each cohort will be balanced with one subject receiving active IMP and one receiving placebo. The allocation for the main group of each cohort will be unbalanced with 5 subjects receiving active IMP and 1 subject receiving placebo.

A treatment allocation list will be produced prior to dosing using the randomisation schedule and will be retained in the ISF.

#### 8.8.3 Blinding

This is a double-blind study. Treatment assignment will not be known to the subjects, the sponsor or the staff who are involved in the clinical evaluation of the subjects and the analysis of data. The randomisation schedule and disclosure envelopes will be generated by an unblinded statistician at Quotient Sciences according to Quotient Sciences SOPs. The unblinded statistician will not be involved in any decisions relating to populations for analysis prior to unblinding.

Prior to database lock and unblinding, all original randomisation materials, including the original final signed and dated randomisation schedule, will be held by the Quality Assurance (QA) department at Quotient Sciences. The Data Sciences department will not have access to the randomisation schedule before database lock and unblinding.

Interim PK parameter estimations will be performed using bioanalytical data applied with subject aliases in order to maintain the study blind.

There may be instances where interim PK data have the potential to be treatment revealing eg missed blood sampling occasions. In these cases, every effort will be made by the pharmacokineticist to maintain the study blind by appropriate presentation of data to the study team. Data demonstrating extremes of exposure will always be presented, regardless of the potential to reveal the study blind.

The unblinded Qualified Person (QP) or designee at the clinical site will receive a copy of the final randomisation schedule for preparation of the study drug and preparation of the treatment allocation list. A copy of the randomisation schedule will also be made available to the laboratory performing the bioanalysis to allow selective analysis of drug concentrations and to the pharmacovigilance provider for potential safety reporting. Two sets of disclosure envelopes (ie sealed envelopes containing individual subject randomisation details) will be provided. One set will be held in the clinical area and the other retained in the ISF. These may be used in the event of an emergency by the investigator. Any request for information on the randomisation schedule after initial issue must be made using a randomisation disclosure form, except in the case of emergency unblinding, which must be recorded on the emergency unblinding form. Access to study drug assignment will be immediately available if the investigator deems it necessary to break the study blind in the interest of a subject's medical safety, in case of a medical emergency, or if warranted during scheduled safety reviews. The sponsor medical responsible and the sponsor project manager must be contacted within 24 h following disclosure of study drug assignment.

Details of any disclosure of the randomisation schedule will be documented and retained in the ISF. The sponsor will be notified if the study blind is broken.

The study blind will be broken after the study database has been locked and the safety population has been defined. Any subsequent request for issue of the randomisation schedule prior to unblinding must be made using a randomisation disclosure form.

